## 1 PROTOCOL SUMMARY

### 1.1 SYNOPSIS

Title:	Postpartum progestin-only pill use and breastfeeding study
Study Description:	This study will assess the impact of early initiation (less than one week postpartum) and delayed initiation (4 weeks postpartum) of two types of progestin-only contraceptive pills on maternal, breastmilk, and infant outcomes. This is a placebo-controlled randomized controlled trial enrolling dyads of mothers and their newborn babies. We will explore if the type and timing of initiation of pills is acceptable to the user with minimal side effects, impacts the supply or composition of breastmilk, and/or affects infant growth.
Aims:	Specific Aim: To determine whether the type of progestin used (drospirenone in drospirenone-containing progestin-only pills (d-POPs) vs. norethindrone in norethindrone-containing progestin-only pills (n-POPs)) or the timing of progestin initiation (early vs. delayed) affects: Aim 1a Maternal: the duration of exclusive breastfeeding continuation or the rates and types of breastfeeding supplementation over 8 weeks postpartum. Aim 1b Maternal: the proportion of mothers using progestin-only pills at 8 weeks postpartum. Aim 2 Milk: the composition of breastmilk (fat, protein, carbohydrates) at 4 weeks postpartum. Aim 3 Infant: infant growth (weight, length, and head circumference) from birth to 4 weeks.
Study Population:	Postpartum women who delivered an infant within the previous 7 days
Description of Sites	University of California, San Diego (UCSD)
Enrolling Participants:	
Study Duration:	1 year
Participant Duration:	8 weeks

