## 3 OBJECTIVES AND ENDPOINTS

Aim	Variable	Description	Source
Maternal Outcomes			
1a	Breastfeeding	Exclusive breastfeeding : own mother's milk via breast or bottle. Predominant breastfeeding : greater than 75% of the infant's diet is their own mother's milk; the remainder of the diet is formula, donated milk, or other supplemental foods Mixed Breastfeeding : 25-75% or more of the infant's diet is their own mother's milk Predominantly supplementing : <25% diet is breastmilk No breastfeeding : infant is not consuming own mother's milk	End of weeks 2-8
1a	Supplementation type	Donated breastmilk, formula, other milks (cow, plant-based, nut), juice, water, cereal, other foods	End of weeks 2-8
1b	Progestin-only pill use	Any use, timing of initiation of POP use (assigned), type of POP (assigned), number of missed pills	End of weeks 2-8.
1b.	Contraception use	Sterilization (male and female), intrauterine devices, subdermal implants, oral contraceptives (combined), condoms (male and female), injectables, emergency contraceptive pills, patches, diaphragms, sponges, cervical caps, spermicidal agents, vaginal rings, withdrawal, fertility awareness, abstinence, and LAM	4 and 8 weeks
	Vaginal bleeding	Number of days of any bleeding and spotting in last month	Estimated at 4 and 8 weeks
	Satisfaction with contraception	Satisfied with method, would recommend method to a friend	4 and 8 weeks
	Pregnancy	Self-reported new pregnancy, pregnancy intendedness, whether planning to continue the pregnancy or not, and pregnancy outcome: continued, terminated, pregnancy loss	4 and 8 weeks
Milk Outcomes			
2	Composition of breastmilk	Fat, protein, carbohydrate (including oligosaccharide) content of milk	4-week breastmilk sample
	Maternal perception of adequate milk supply	Hill and Humenick Lactation Scale	End of weeks 2-8
Infant Outcomes			
3	Change in infant growth	Weight, length, and head circumference	Change between baseline and 4 weeks

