#### **Enrollment Procedures:**

We will assess women who indicate that they desire POPs for contraception for eligibility after they have received contraceptive counseling. Research staff will identify postpartum women who are planning on utilizing POPs as postpartum contraception via review of medical records of patients receiving inpatient obstetrical services at UCSD. Study staff will visit these potential participants during their inpatient hospital stay to present the study and administer the pre-screening eligibility form if the patient is interested in participation. While only women who intend to use POPs for at least 8 weeks will be enrolled, all participants will be told if they are unhappy with POPs at any time, the study team will facilitate timely contraceptive counseling and referral to an appropriate provider to ensure that they can switch contraceptive methods at any time if they choose.

After enrollment and prior to randomization, participants will be asked to complete a brief self-administered demographic questionnaire using a private secure tablet that enters data directly into REDCap (Research Electronic Data Capture), a secure electronic data collection system. Demographic characteristics collected will include maternal age, race, Body Mass Index, gestational weight gain, parity, education, previous experience breastfeeding, previous contraceptive use history, breastfeeding intentions, delivery type and complications, infant stay in neonatal intensive care unit (and length of stay), infant birth weight, race, sex assigned at birth, and gestational age at birth. Participants will receive a gift card via text or email link for completing the survey.

[figure not shown]

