#### **Breastmilk collection and analysis:**

Women will attend an in-person visit at 4 weeks PP with their infant. Participants will have the option to collect a mid-feeding sample at home with all pumping materials and instructions sent to her home or collect a sterile sample at the visit using a study-provided breast pump. 10 mLs of breastmilk from the collection (either refrigerated sample brought to the visit or collected on-site) will be frozen at the site of the visit at the research site. The milk samples will be frozen at -80 degrees onsite. The lab will use liquid chromatography to assess the composition of breast milk and compare the concentrations of total fat, total protein and carbohydrates including oligosaccharides.

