### 9.4.5 BASELINE DESCRIPTIVE STATISTICS

Baseline characteristics such as demographic information (age, education level, race, ethnicity and employment status) will be collected. At the time of enrollment, questions will also be asked about pregnancy history, past use of contraception, use of donor milk and current perception of adequacy of

human milk supply. Means and proportions of respondents in each of the two groups will be compared to assess for success of randomization.

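### Aim 3 infant growth has two different starting points and only one named starting value, and no infant measurement is described at 4 weeks

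*Combined protocol and SAP*

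**What the plan says.** **Endpoint.** Section 1.1 gives Aim 3 as "infant growth (weight, length, and head circumference) from birth to 4 weeks". The table in Section 3 lists the same components, "Weight, length, and head circumference", and times them as "Change between baseline and 4 weeks". That entry stands in the Source column but gives timing only. It does not say who measures the infant or which record is used. Baseline is not defined anywhere in the document.

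**Start.** Under Enrollment Procedures (Section 8.1) the mother fills in a "brief self-administered demographic questionnaire" after enrolment and before randomization. Its item list ends "infant birth weight, race, sex assigned at birth, and gestational age at birth". Section 9.4.5 says "Baseline characteristics such as demographic information (age, education level, race, ethnicity and employment status) will be collected" and goes on to pregnancy and contraceptive history, donor milk and perceived milk supply. It names no infant size measure. Medical records are mentioned as the way to find candidates, "via review of medical records of patients receiving inpatient obstetrical services at UCSD", and not as a source of infant data.

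**Four weeks.** The milk-collection part of Section 8.1 states: "Women will attend an in-person visit at 4 weeks PP with their infant". The rest of that part concerns the milk sample, and the Surveys part adds a tablet questionnaire at the visit. No window is given for the visit, and Section 7.3 allows a missed visit to be rescheduled.

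**Analysis.** Section 9.4.3 plans ANOVA across the three groups and t-tests for pairs, with no covariates.

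**The concern.** A change score needs a defined start, a defined end and a source for each. Here the start is worded in two ways, and the procedures do not say how most of the values are obtained. Staff following the written procedures could reach the analysis with a mother-reported birth weight and nothing to pair it with. Two people reading the two definitions could also build different change scores.

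This matters more than Aim 3's secondary status suggests. Section 2.2 names infant growth among the reasons for the current cautious classification of early progestin use, faults earlier studies for not using validated outcome measures, and presents this pilot as groundwork for a large trial. A pilot that does not set down how growth is measured cannot show that the procedure works. Measurements missed at 4 weeks cannot be recovered later.

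**Working it through.** The plan gives no standard deviation, effect size, alpha or power for growth, so it has no figure of its own to reproduce. The check is a comparison of the text, followed by simple arithmetic on the intervals.

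**1. What the readable procedures cover**

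| Measure | Starting value named | 4-week measurement described | Both ends described |
|---|---|---|---|
| Weight | Yes (birth weight, maternal questionnaire) | No | No |
| Length | No | No | No |
| Head circumference | No | No | No |
| Total | 1 of 3 | 0 of 3 | 0 of 3 |

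**2. How far the two origins can differ**

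Inputs: enrolment can occur up to 168 hours after delivery (Section 5.1). The end is taken as exactly day 28, which is an assumption because no window is stated; 28 × 24 = 672 hours. With b the infant's age in hours at the start, interval = (672 − b) / 24 days.

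- Origin at birth, b = 0: 672 / 24 = 28 days.
- Origin at the latest enrolment, b = 168: 504 / 24 = 21 days.
- Ratio: 21 / 28 = 75%, so the largest shortfall is 7 / 28 = 25%.

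Under an enrolment origin, the birth weight on the questionnaire would not be the baseline weight either.

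**3. Share of a birth-origin interval before any study pill**

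Share = start of pills / 672 hours.

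- 120 hours (Section 6.1 and Randomization): 120 / 672 = 17.9%.
- 160 hours (upper limit in Section 6.1): 160 / 672 = 23.8%.
- 168 hours (upper limit under Randomization): 168 / 672 = 25.0%.

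The two upper limits contradict each other and must be reconciled, but the difference barely affects this point.

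**4. Movement at the other end**

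Section 7.3 can be read as letting a missed visit take place up to a week later, or only as asking that contact be attempted within a week. On the first reading the infant could be 28 + 7 = 35 days old, 7 / 28 = 25% beyond the nominal interval. A birth origin therefore does not by itself make intervals equal.

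**5. Price of adjustment**

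With 30 infants in three arms of 10, all measured, one-way ANOVA has 30 − 3 = 27 residual degrees of freedom. Adding birth value and age leaves 25. A two-arm comparison has 10 + 10 − 2 = 18, which becomes 16.

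**The case against.** The strongest reply is that Section 3 does plan all three measures at two time points, so what is missing is the procedure and not the intention. The enrolment list describes a demographic questionnaire and says what it will include, so it need not be the whole baseline dataset. The figure at the end of Enrollment Procedures and the content of Figure 2, on outcome evaluation, were not available and might show infant measurements. All of this stands. A reader might infer that length and head-circumference change cannot be computed while weight change can. The documents support neither half: nothing says those values go uncollected, and weight has no described 4-week measurement either.

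A second reply is that baseline can simply be read as birth, since birth weight is the only starting value named. That is the natural reconciliation, but the text does not make it, and a figure would not necessarily settle the wording.

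A third reply concerns the 21-to-28-day range, which is an outer bound. Women are approached during the hospital stay, so most enrolments are probably earlier and closer together than the 168-hour ceiling allows, although no length of stay is given. A reader might also infer that uneven intervals bias the comparison. They do not in expectation: enrolment comes before randomization, so age at enrolment is unrelated to arm apart from chance.

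Finally, Aim 3 is not the primary outcome (Section 9.1), and N = 30 was chosen for feasibility (Section 9.2). That limits the weight of the point without removing it.

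**Conclusion.** The point holds as a gap in definition and procedure, together with an analysis that could be more precise. The origin is worded in two ways, and one of the two terms is undefined. The readable procedures name 1 of 3 starting values, by maternal report, and describe 0 of 3 measurements at 4 weeks. The planned tests make no allowance for age at measurement, and the visit has no stated window.

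The consequence is possible missing or inconsistent growth data and avoidable noise with 10 infants per arm. It is not demonstrated bias, and it is not proof that any endpoint is beyond computing. The 25% figure is an extreme that requires an enrolment origin, enrolment spread over the full 168 hours and a visit on day 28 exactly. It cannot be turned into a loss of power, because the documents give no variability or growth rate. The conclusion also assumes that the unavailable figures do not supply the missing procedures. If they do, the conflict over the origin and the unadjusted analysis would remain unless those figures also settle them. The change should be made, but the trial does not depend on it.

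**What to change.** 1. Use one origin in Sections 1.1 and 3. Birth is the practical choice because it matches the only starting value now named. Note that the first 5 to 7 days then precede any study pill in every arm.
2. Take birth weight, length and head circumference from the newborn record instead of maternal report, and say so in Section 8.1. This assumes that the record holds all three. The protocol should add this use of records, since it currently mentions them only for finding candidates.
3. State that all three are measured at the 4-week visit, by whom and how. Research staff are already blinded. State the visit window as well.
4. Record exact infant age at measurement. In Section 9.4.3, replace the unadjusted ANOVA and t-tests for growth with ANCOVA on birth value and age. Adjusting for age at the visit assumes that the arm does not influence when the visit occurs, which blinding makes reasonable.

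The cost is a few fields of chart abstraction per infant, a few minutes at a visit the infant already attends, and one or two degrees of freedom. No arm, dose or sample size changes.

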#### **Randomization:**

A licensed medical provider on the clinical care team will review eligibility for the method and instruct patients on use of POPs prior to discharge from the hospital and will approve a prescription for both POPs. Participants will then be randomized to (1) early d-POPs to be initiated at 120-168 hours (5-7 days) after delivery, (2) early n-POPs to be initiated at 120-168 hours after delivery, or (3) placebo for 28 days followed by d-POPs initiated at 4 weeks (28-35 days) after delivery, at a 1:1:1 ratio (Figure 2). Study staff will then provide participants with written and verbal instructions about when to initiate the method and to take the study medications in the order dispensed. Participants, care providers, and research staff will be blinded to group assignment. Participants will be instructed on lactational

amenorrhea method (LAM), a highly effective form of contraception, and will be counseled that if they no longer meet criteria for LAM, then they may be at risk for unintended pregnancy between days 28 and 33 and should use condoms or abstain from intercourse during that time. Before day 28, the CDC Selected Practice Recommendations state that a provider can be “reasonably certain that woman is not pregnant” regardless of LAM use and after day 33 all study drugs will be effective contraception regardless of group assignment.

The research team will dispense two 28-day pill packs containing either d-POPs, n-POPs, or one placebo and one d-POPs, as determined by the randomization scheme, and labeled 1st and 2nd. For participants in group 3, the first pack will contain only placebo to facilitate delayed initiation while ensuring blinding. D-POP packs will include 24 active and 4 placebo tablets per month, and n-POP packs will include 28 active tablets, packaged in order of daily use. All d-POP, n-POP, and placebo tablets will be encapsulated by the research pharmacies to have an identical appearance.

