## 6 STUDY INTERVENTION

### 6.1 STUDY INTERVENTION

Group 1: Initiation of d-POPs 120-160 hours after delivery (N=10)

Group 2: Initiation of n-POPs 120-160 hours after delivery (N=10)

Group 3: Initiation of d-POPs 4 weeks after delivery (N=10) [placebo starting 120-160 hours, continuing for 28 days]

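### The back-up contraception advice ends at day 33, but Group 3 may take its first d-POP capsule as late as day 35

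*Combined protocol and SAP*

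**What the plan says.** The relevant text is in section 8.1 under Randomization, with the group definitions in section 6.1.

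- **Advice.** Women who stop meeting the LAM criteria are told that "they may be at risk for unintended pregnancy between days 28 and 33 and should use condoms or abstain from intercourse during that time".
- **Reason for the end date.** The protocol states that "after day 33 all study drugs will be effective contraception regardless of group assignment".
- **Start of capsules in the early arms.** Group 1 is described as "early d-POPs to be initiated at 120-168 hours (5-7 days) after delivery", and Group 2 has the same hours.
- **Group 3.** Section 8.1 describes "placebo for 28 days followed by d-POPs initiated at 4 weeks (28-35 days) after delivery". Section 6.1 gives "placebo starting 120-160 hours, continuing for 28 days".
- **Packs.** Each woman receives two 28-day packs and is told to "take the study medications in the order dispensed". For Group 3, "the first pack will contain only placebo to facilitate delayed initiation while ensuring blinding".

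Nothing elsewhere in the document lengthens the advice for women who start after day 5.

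**The concern.** Section 8.1 appears to contradict itself. It allows Group 3 to begin d-POPs as late as day 35, yet says every arm is protected once day 33 has passed. A woman whose first active capsule is due on day 34 or 35 cannot have been protected by it before then.

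What is at stake is participant safety. Participants, care providers and research staff are all blinded, so nobody in contact with a Group 3 woman can tell her that she is still on placebo. She could stop back-up while following the advice correctly. The protocol treats this period as one of real risk: section 2.2 describes the LAM criteria as strict, says pregnancy is hard to exclude beyond 4 weeks without them, and reports that more than half of women have resumed intercourse by 6 weeks. Some women will foreseeably lose LAM protection, since LAM requires exclusive breastfeeding and the primary outcome in section 9.1 is whether that continues to 8 weeks.

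**Working it through.** **Inputs**

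- First capsule: 120-168 hours after delivery (section 8.1, written for the early arms; taken here to apply to pack 1 in all arms because of blinding) or 120-160 hours (section 6.1, written for Group 3).
- Placebo: 28 daily capsules, all taken before the second pack (sections 6.1 and 8.1).
- Day count: section 8.1 equates 120-168 hours with 5-7 days, so days are elapsed days (hours/24).
- Stated end of the advice: day 33.

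**Formulas**, for a first capsule at hour h:

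- last placebo day = h/24 + 27
- first d-POP day = h/24 + 28

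**Reproducing day 33.** The protocol does not show how it reached this figure. The earliest permitted start gives it exactly: 120/24 + 28 = 5 + 28 = 33.0. No later permitted start does.

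**Gap between the end of the advice and the first d-POP capsule.** The wording allows two readings of the end date:

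- Reading A: the interval ends at day 33.0. Gap = max(0, first d-POP day − 33.0).
- Reading B: day 33 is inside the interval, which ends at day 34.0. Gap = max(0, first d-POP day − 34.0).

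| First capsule (h) | Start day | Last placebo day | First d-POP day | Gap, A (days) | Gap, B (days) |
|---|---|---|---|---|---|
| 120 | 5.00 | 32.00 | 33.00 | 0 | 0 |
| 144 | 6.00 | 33.00 | 34.00 | 1.00 | 0 |
| 160 (latest, 6.1) | 6.67 | 33.67 | 34.67 | 1.67 | 0.67 |
| 168 (latest, 8.1) | 7.00 | 34.00 | 35.00 | 2.00 | 1.00 |

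**Share of the permitted start window affected**

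- Reading A: every start after 120 hours.
- Reading B: starts after 144 hours. That is (168 − 144)/(168 − 120) = 24/48 = 50% of the section 8.1 window, or (160 − 144)/(160 − 120) = 16/40 = 40% of the section 6.1 window.

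These are shares of hours, not of women. The documents do not say when within the window women start.

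**Other points checked**

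- Calling the day of delivery day 1 would move the first d-POP capsule to days 34-36, which widens the gap. The hours-to-days conversion in section 8.1 points to elapsed days in any case.
- Stopping placebo at day 28 after delivery would not fit a full 28-capsule pack taken in order.
- The lower part of the stated 28-35 day window (days 28-32) cannot be reached with 28 placebo days from day 5 or later.
- No time is allowed above for the pill to take effect, because the documents give none. If 0 to 7 days is assumed, protection after the latest start would begin between day 35 and day 42.

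**The case against.** The strongest reply is that the gap is small and depends on how days are counted. The wording most naturally means that day 33 is covered and the assurance starts on day 34, which is Reading B; the 2.0-day figure and the claim that every start after 120 hours is affected belong only to Reading A. In completed whole days, a start at 144-167 hours is day 6 and the first d-POP capsule falls on day 34, the first day after the advice ends. On that count no start in the section 6.1 window leaves a whole placebo-only day uncovered, and only a start at 168 hours does. The 168-hour limit is itself written for Groups 1 and 2.

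Exposure is also narrow. It requires assignment to Group 3, a late start, loss of LAM, and stopping back-up within a short interval. Women are enrolled because they intend to breastfeed exclusively. The written and verbal participant instructions mentioned in section 8.1 are not available here and may be more exact.

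Much of this stands as a limit on size: Reading B is the better central reading, and A is the upper bound. It does not remove the contradiction. Section 8.1 itself allows d-POP initiation to day 35, and the section 6.1 window still reaches day 34.67. Even on the whole-day count, a woman taking her first d-POP capsule on day 34 has been told that it already protects her. The in-person visit at 4 weeks could have been used to repeat or adjust the advice, but no such counselling is specified.

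**Conclusion.** The concern holds: the protocol's day 33 is the earliest day on which a Group 3 woman can take her first d-POP capsule, and it is used as the day by which all women are covered. The uncovered interval is at most 1.0 day on Reading B and 2.0 days on Reading A (0.67 and 1.67 days under the section 6.1 window), before any allowance for onset of effect.

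This rests on elapsed-day counting, daily capsules with none missed, and pack 1 being finished before pack 2. It concerns only Group 3 women who start late enough and no longer meet the LAM criteria. Their number cannot be estimated from the documents; the 10 women planned for Group 3 are an upper bound. The absolute risk is small, but the error runs in the unsafe direction and the woman exposed cannot detect it. No sample size, endpoint or analysis is affected, and the finding is about the protocol text only.

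**What to change.** **Needed**

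- In section 8.1, extend the condom or abstinence advice to at least day 35, in identical words for all arms. Day 35 covers both start windows.
- Have the responsible clinicians decide whether to add time for onset of effect, and state the resulting day.
- Correct the sentence that all study drugs are effective after day 33, and any participant instructions that repeat it.

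**Worth doing at the same time**

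- Use one start window in sections 6.1 and 8.1 (160 or 168 hours).
- Restate Group 3 d-POP initiation as days 33-35, or as days 33-34.67 if 160 hours is kept. The label of 4 weeks for delayed initiation in the synopsis and section 6.1 would need a matching clarification.

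**Cost.** The needed change is one date in two sentences plus any matching participant text; the other edits touch a few more lines. Before any onset allowance, women who no longer meet the LAM criteria would be asked for up to 2 more days of condoms or abstinence. Blinding is preserved because the wording does not differ by arm.
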